
such that negative scores indicate decreased knowledge, and positive scores indicate increased knowledge from pre to post DA (zero = no change). From a linear regression model for the outcome of change in knowledge, we will test the effect of REDS overall and domain scores. We will also assess the association between post-test knowledge and REDS scores. SH6: Perceived screening benefits will decrease from pre- to post-DA; perceived screening harms will increase. REDS responses will be associated with less change from pre- to post-DA. • Analysis: Paired t-tests will be used to examine mean difference in perceived screening benefits and harms pre-DA versus post-DA. A difference score will be computed for perceived benefits and harms: post-DA minus pre-DA, such that negative scores indicate decreased perceived benefit/harm, and positive scores indicate increased perceived benefit/harm from pre to post DA (zero = no change). From a linear regression model for the outcome of change in perceived benefits/harm, we will test the effect of REDS overall and domain scores. SH7: REDS are predicted to reflect a more emotion-laden set of reactions, whereas perceived discordance with prior knowledge is conceptualized as a more cognitive reaction. Therefore, REDS will be associated with emotional responses to the DA (anger, anxiety), whereas perceived discordance with prior knowledge will not be associated with emotional responses to the DA (after adjusting for REDS). • Dependent variables: Emotional responses (anger, anxiety) • Independent variables: overall REDS score [Continuous]; Bayesian updating [Continuous] • Analysis: In separate linear regression models for each of the emotional response items, we will test the effect of REDS score and discordance (Bayesian updating)

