### Data collection procedures

Participants will be recruited through Ipsos.

*No files selected*

Sample size

Our expected sample size is 500 participants.

Sample size rationale

The study was powered to detect an interaction between objective cancer risk and REDS on receipt of screening (Aim 2). We estimated power by simulation based on 2000 data sets using R statistical software. We use a logistic regression model for the outcome of screening (yes/no) with fixed effects for REDS (high/low) and objective cancer risk (continuous) and their interaction. Assuming that there is a probability of 50% of high REDS (treated as a binary variable), a sample size of 500, and that 10% of variability is explained by other factors in the model (confounders), we would be able to detect a difference in the log odds of -0.3 with 90% power (alpha=0.05). Thus, if the odds of the outcome is 1 in the low REDS group, for every unit increase in cancer risk we can detect an odds of 0.74 (=exp(0-0.3)) in the high REDS group (i.e., an odds ratio of 1.35). Additionally for the outcomes in Aim 1, with a sample size of N=500 we will be able to estimate the prevalence of REDS with a margin of error of 2.8-3.0% depending on the actual prevalence 30-70%. The sample size of 500 will also allow us to detect an increment of 1.2% in variability explained in the linear regression models assuming other factors explain 20% of the variability with 80% power (alpha=0.05).

Stopping rule

We have contracted with Ipsos to collect 500 participants.

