#### Inference criteria

We will use the standard  $p < 0.05$  criteria for assessing statistical significance. We will adjust for multiple comparisons when testing the same hypotheses across the multiple domains of screening benefits, overdiagnosis, and false positives.

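### SH7 predicts that discordance is unrelated to emotion, but p<0.05 per coefficient can neither support that absence nor show that REDS and discordance differ

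*SAP*

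**What the plan says.** SH7 is listed in the SAP's Hypotheses section among the other secondary hypotheses and is repeated in the Analysis Plan. It has two halves. REDS, regarded as emotion-laden, should be associated with anger and anxiety. Discordance with prior knowledge (the Bayesian updating score), regarded as cognitive, should not: "perceived discordance with prior knowledge will not be associated with emotional responses to the DA (after adjusting for REDS".

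The stated analysis is: "In separate linear regression models for each of the emotional response items, we will test the effect of REDS score and discordance (Bayesian updating". Overall REDS and discordance are both listed as continuous predictors of each emotional item.

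The Inference criteria section gives p<0.05 as the "criteria for assessing statistical significance". It adds: "We will adjust for multiple comparisons when testing the same hypotheses across the multiple domains". It contains nothing on how a predicted absence of association is to be judged: no smallest association of interest, no equivalence margin, no confidence-interval rule and no test that two coefficients differ.

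On size, the SAP states: "Our expected sample size is 500 participants". Its only power figure for linear models concerns detecting an increment in explained variance.

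**The concern.** Two separate inferences are at risk.

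1. **Absence.** With p<0.05 as the only rule, the sole result that can favour the second half of SH7 is a non-significant discordance coefficient. That result also arises when a modest association exists and the estimate is too imprecise to show it. H1 predicts that REDS and discordance are correlated, and the stronger that correlation, the wider the interval for discordance once REDS is in the model.

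2. **Contrast.** The substantive claim is comparative: REDS is the emotional reaction and discordance the cognitive one. Comparing two p-values does not test that. One coefficient can fall just beyond the threshold and the other just short of it while the difference between them is well within chance.

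What is at stake is the SAP's conceptual distinction between its main outcome and its main cognitive predictor. No primary hypothesis depends on it.

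**Working it through.** **The plan's own figure.** The SAP's sample size rationale says N=500 can "detect an increment of 1.2% in variability explained in the linear regression models", "assuming other factors explain 20% of the variability with 80% power (alpha=0.05". Check with a 1-df F test:

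- f² = 0.012/(1 − 0.20 − 0.012) = 0.01523, and the noncentrality is 500 × 0.01523 = 7.61.
- Power is 78.6%. The increment that gives exactly 80% is 1.24%.

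The stated 80% is reproduced to within 2 points, so there is no arithmetic fault. The figure concerns detection, however. On the same calculation, a real increment of 1.2% is non-significant about 21% of the time, 0.6% about 51%, 0.4% about 65% and 0.2% about 80%.

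**Inputs for the SH7 model.**

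- N = 500 and alpha 0.05 are from the SAP. Two-sided testing is assumed, because sidedness is not stated.
- Model R² = 0.20 is assumed. It echoes the 20% in the sample size rationale but is not given for SH7.
- The REDS-discordance correlation r is predicted to be positive under H1, with no size given. The range 0.3 to 0.8 is assumed.
- Equivalence margins of 0.10 and 0.15 are illustrations only. The documents give none.

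**Formulas** (two standardised predictors, normal approximation with t critical values 1.965 and 1.648):

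- SE = √[(1 − R²)/((N − 3)(1 − r²))]. For r = 0.7: √[0.80/(497 × 0.51)] = 0.0562.
- P(non-significant | β) = 1 − Φ(β/SE − 1.965) − Φ(−β/SE − 1.965). For β = 0.10 and r = 0.7: 0.10/0.0562 = 1.78, which gives 57%.
- Power to show equivalence at a true zero (90% CI inside ±m) = 2Φ(m/SE − 1.648) − 1, set to 0 if negative. For m = 0.15 and r = 0.7: 2Φ(1.02) − 1 = 69%.

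| r | SE | 95% half-width | Non-sig. at β=0.10 | at 0.15 | at 0.20 | Equivalence power, m=0.10 | m=0.15 |
|---|---|---|---|---|---|---|---|
| 0.3 | 0.042 | 0.083 | 34% | 5% | 0% | 53% | 94% |
| 0.5 | 0.046 | 0.091 | 42% | 10% | 1% | 39% | 89% |
| 0.7 | 0.056 | 0.110 | 57% | 24% | 6% | 11% | 69% |
| 0.8 | 0.067 | 0.131 | 68% | 39% | 15% | 0% | 45% |

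These rates are per model. SH7 names two emotions, so the chance that both discordance coefficients are non-significant is lower. At r = 0.7 and β = 0.10 in both models it would be 0.57² ≈ 33% if the two tests were independent, and nearer 57% if they were strongly correlated.

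Exclusions for failing both attention checks would raise the rates. With N = 400 (assumed) and r = 0.7, the figures for 0.10 and 0.15 become 65% and 34%.

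**The contrast.** In a two-predictor model the two standardised coefficients have the same SE and their sampling correlation is −r, so SE(difference) = SE × √[2(1 + r)]. Take r = 0.6, where SE = √[0.80/(497 × 0.64)] = 0.050, and suppose the estimates are 0.18 for REDS and 0.09 for discordance:

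- REDS: 0.18/0.050 = 3.6, significant.
- Discordance: 0.09/0.050 = 1.8, not significant.
- Difference: 0.09/(0.050 × √3.2) = 0.09/0.089 ≈ 1.0, so the data do not distinguish the two.

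Both halves of SH7 would appear to be met in data that do not separate the constructs.

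**The case against.** A reader might infer that the SAP treats a non-significant discordance coefficient as proof of its theory. The SAP does not say so. It says only that both effects will be tested. That non-significance would count as support follows from the absence of any other rule, and support is weaker than proof.

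A reader might also infer that collinearity tilts SH7 as a whole towards success. It does not. SH7 needs REDS to be significant as well, and with two predictors the inflation is the same for both. Power for a standardised REDS coefficient of 0.15 falls from 96% at r = 0 to 85% at r = 0.6 and 61% at r = 0.8. Collinearity makes the null half easier and the other half harder. If the REDS coefficient is large, though, that loss is small and the null half is still the easier one to obtain.

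Further points have weight. SH7 is secondary. At N = 500, coefficients of 0.20 or more are seldom missed unless r is near 0.8. H3 and SH3 in the Hypotheses section also predict non-significance, so one general rule for predicted nulls could serve all three. Such a rule would not supply the REDS-versus-discordance contrast, which needs SH7's own models and outcomes.

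Nor does an equivalence rule answer everything. A margin of 0.15 accepts 0.10 as negligible by definition, so the margin must reflect what the investigators regard as too small to matter. The SAP's check of variance inflation is written for the SH1 model and would probably not flag the problem here: r = 0.8 gives a VIF of only 1/(1 − 0.64) = 2.8.

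**Conclusion.** The concern holds in limited form. The SAP gives SH7 no criterion that could support a predicted absence of association, and no test of the contrast on which its interpretation rests. The consequence is confined to small associations. A true coefficient of 0.10 would be non-significant in about 34% to 68% of data sets per model, and 0.15 in 5% to 39%, while 0.20 is missed in at most 15%.

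These figures rest on an assumed R² of 0.20 and an assumed r of 0.3 to 0.8. The SE scales with √(1 − R²), so R² of 0.10 multiplies it by √(0.90/0.80) = 1.06 and R² of 0.30 by √(0.70/0.80) = 0.94. The conclusion does not depend on the exact values. The primary hypotheses and the stated sample size are unaffected.

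**What to change.** Add to the SH7 analysis text, before the data are analysed:

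1. In each emotional-response model, standardise both predictors, test the difference between the REDS and discordance coefficients, and report it with a confidence interval. Base the emotional-versus-cognitive claim on this contrast.
2. Report the discordance coefficient with its confidence interval whatever its p-value.
3. State that discordance is not associated with an emotion only if the 90% confidence interval lies wholly within a smallest association of interest. The investigators should choose and justify that value in advance, since the documents supply none.
4. Otherwise describe a non-significant discordance coefficient as inconclusive.

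The cost is a few sentences of SAP text and one linear contrast per model already planned, with no new data. The downside is that the answer may be inconclusive. With an illustrative margin of 0.15, equivalence power at a true zero is about 94% / 89% / 69% / 45% for r = 0.3 / 0.5 / 0.7 / 0.8, and with 0.10 it is 53% or less. The contrast is also less precise than either coefficient: at r = 0.7 its SE is 0.056 × √3.4 ≈ 0.10. If the two scores prove highly correlated, this sample may not separate them, and the report should say so.

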## Study Information

### Hypotheses

**SPECIFIC AIM 1: Predictors of REDS PRIMARY HYPOTHESES:** H1: Perceived discordance with prior knowledge will predict REDS. We developed an assessment of the degree to which the DA information conflicts with prior knowledge. We predict that when the DA information conflicts with an individuals' prior knowledge about BCS, they will express more disbelief, reactance, self-exemption, and source derogation. H2: Perceived threat and screening efficacy will predict REDS. We derive our predictions from the Extended Parallel Process Model (EPPM) which is an extension of the fear appeal model. The EPPM proposes that people are most likely to reject information when they feel threatened AND feel they cannot do anything to address the threat (i.e. a high threat, low efficacy message). We predict that women who perceive high affective cancer risk AND have high preexisting expectations for screening will express the strongest reactance, self-exemption, disbelief and source derogation (because they experience the DA as a high threat, low efficacy message). We will test this hypothesis by examining pre-test screening expectations (perceived screening benefit minus perceived harm), and pre-test affective cancer risk perceptions, as predictors of "REDS" outcomes. H3: Perceived threat and screening efficacy will predict information rejection after controlling for discordance with prior knowledge. Putting predictors from H1 and H2 together in a model, discordance with prior knowledge will no longer be a significant predictor of REDS whereas affective cancer risk and preexisting expectations of screening will continue to be significant predictors. **SECONDARY HYPOTHESES:** SH1: Other significant predictors of REDS responses will include: 1. stronger injunctive norms (i.e. people think I should screen), 2. Medical maximizing (vs. minimizing), 3. Prior screening use (yes/no), 4. Have friends or family diagnosed with breast cancer (vs. not), 5. Lower pre-test trust in the healthcare system, 6. Viewing screening as a protected value (i.e. moral imperative). We predict that all of these variables will show significant bivariate correlations with REDS responses but we do not have specific hypotheses about which will be significant in a model including all predictors. SH2: Relative to White women, Black women will express more self-exemption (feeling that the information does not apply to them) but not necessarily more disbelief, reactance or source derogation. Our rationale for using race as a predictor is that, due to longstanding health disparities related to insufficient care among minority women, and a historic lack of inclusion of BIPOC individuals in clinical trials, Black women will be more likely than White women to believe that the information does not apply to them. SH3: Factors that will not significantly predict REDS will include: 1. Insurance status, 2. Structural barriers, 3. Pre-test knowledge. **SPECIFIC AIM 2: Predictors of screening intentions** H4: There will be an association between objective cancer risk and screening intentions such that women at higher cancer risk will be more likely to intend to screen before 50 (vs. wait to screen or not screen at all). H4a: There will also be an interaction such that women with lower REDS responses will show a stronger correlation between objective cancer risk and screening intentions, and women with higher REDS will show smaller or null correlations between objective risk and intentions. H5: There will be an association between post-DA knowledge and

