
screening intentions such that women with lower post-DA knowledge will be more likely to intend to screen before 50. H5a: There will also be an interaction with REDS such that women with lower REDS responses will have a stronger correlation between knowledge and intentions, and women with stronger REDS will show smaller or null correlation between knowledge and screening intentions. Other secondary hypotheses related to the effect of the DA and the nature of REDS: SH4: Trust in the healthcare system will decrease from pre- to post-DA. This effect will be stronger for women with greater REDS responses. SH5: Screening knowledge will improve from pre- to post-DA. REDS responses will be associated with less knowledge increase from pre to post-DA, and will be associated with less total knowledge post-DA. SH6: Perceived screening benefits will decrease from pre- to post-DA; perceived screening harms will increase. REDS responses will be associated with less change from pre- to post-DA. SH7: REDS are predicted to reflect a more emotion-laden set of reactions, whereas perceived discordance with prior knowledge is conceptualized as a more cognitive reaction. Therefore, REDS will be associated with emotional responses to the DA (anger, anxiety), whereas perceived discordance with prior knowledge will not be associated with emotional responses to the DA (after adjusting for REDS).

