## Analysis Plan

Statistical models

H1. Perceived discordance with prior knowledge will predict REDS. • Dependent variable: Overall score averaged across REDS domains [Continuous] • Independent variable: Bayesian updating (4 items) averaged [Continuous] • Hypothesis: Higher (more negative) scores on conflicts with prior knowledge (Bayesian updating) will be correlated with higher (more negative) scores for other domains • Hypothesis: Higher correlation for the benefits domain than the other two domains (overdiagnosis and false positives) • Analysis: Compute bivariate correlation between these two scores within each informational domain; No plans to adjust for covariates in this analysis. Fit linear regression model (correlation) for association between Bayesian updating and REDS. H2. Perceived threat and screening efficacy will predict REDS • Dependent variable: Overall REDS [Continuous] • Independent variable: Pre-test perceived threat (average of 3 affective risk questions; should have high reliability) [Continuous] • Independent variable: Pre-test screening efficacy (questions on how beneficial and harmful is screening) = (perceived benefit – perceived harm) [Continuous] • Hypothesis: Women who perceive high affective cancer risk AND have high preexisting expectations for screening will express strongest (most negative) REDS • Analysis: Linear regression model for overall REDS with interaction term between perceived threat and efficacy (interaction effect indicates that the effect of perceived threat on REDS is modified by screening efficacy) • Interpretation/Visualization: Will make at least one of the variables binary H3. Perceived threat and screening efficacy will predict information rejection after controlling for discordance with prior knowledge (Bayesian updating). • Dependent variable: Overall REDS [Continuous] • Independent variable: Perceived threat (average of 3 affective risk questions) [Continuous] • Independent variable: Screening efficacy (perceived benefit – perceived harm) [Continuous] • Independent variable: Bayesian updating (4 item) [Continuous] • Hypothesis: Contribution of Bayesian updating will be less than the emotional factors • Analysis: In regression model for H2, adjust for Bayesian updating and assess interaction effect and effect of Bayesian updating. Compare to models H1 and H2 and assess whether fit (total variance explained; R-squared) is improved (change in variance when you add the second set of predictors). Perform analysis for each of the domains and see if results are consistent across the domains. SH1: Other significant predictors of REDS • Predictors: 1. stronger injunctive norms (i.e. people think I should screen), 2. Medical maximizing (vs. minimizing), 3. Prior screening use (yes/no), 4. Have friends or family diagnosed with breast cancer (vs. not), 5. Lower pre-test trust in the healthcare system, 6. Viewing screening as a protected value (i.e. moral imperative), 7. Structural barriers, 8. Pre-test knowledge • Analysis: Perform bivariate analyses to assess for the association between the predictors and the REDS. We will also add these variables to the H3 models, to test the unique

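### SH7 leaves the affective risk score out of its models, so part of any REDS–anxiety association may reflect affect already present before the mammography evidence was shown

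*SAP*

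**What the plan says.** The SAP (Hypotheses, SH7) describes REDS as the more emotional kind of reaction and perceived discordance with prior knowledge as the more cognitive kind. It predicts that "REDS will be associated with emotional responses to the DA (anger, anxiety") and that discordance will not be, once REDS is adjusted for.

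The analysis (SAP, Analysis Plan, Statistical models, SH7) lists "Dependent variables: Emotional responses (anger, anxiety") and "Independent variables: overall REDS score [Continuous]; Bayesian updating [Continuous"]. The model statement is "In separate linear regression models for each of the emotional response items, we will test the effect of REDS score and discordance (Bayesian updating"). No baseline emotion, change score or further covariate appears.

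Three other places bear on this:

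- **H2 (SAP, Hypotheses).** It predicts that "women who perceive high affective cancer risk AND have high preexisting expectations for screening will express the strongest reactance" and the other REDS responses. It will examine screening expectations "and pre-test affective cancer risk perceptions, as predictors of" REDS. The Analysis Plan defines the score as "Pre-test perceived threat (average of 3 affective risk questions; should have high reliability").
- **SH4 to SH6 (SAP, Analysis Plan).** Trust, knowledge and perceived benefits and harms are compared before and after the aid and turned into change scores. For SH6: "Paired t-tests will be used to examine mean difference in perceived screening benefits and harms pre-DA versus post-DA".
- **Protocol IV.A (Table 1) and IV.C.** Table 1, presented as covering all survey measures, has no anger or anxiety item. Section IV.C places the affective risk questions after the woman sees her personal risk estimate and before she sees the benefit, false-positive and overdiagnosis evidence.

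**The concern.** SH7 treats anger and anxiety as responses to the aid, but an anxiety rating taken after the aid may also carry affect about breast cancer that was there beforehand. The plan measures something close to that affect, the affective risk score, and H2 expects it to go with higher REDS. If the score also goes with higher anxiety afterwards, it is a common antecedent of both sides of the association SH7 tests, and the SH7 model does not adjust for it. Part of a positive SH7 result could then be H2 seen from another angle.

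What is at stake is interpretation. A significant REDS coefficient would be offered as evidence that REDS are emotional reactions to the evidence, when some or all of it might be explained by affective risk. The argument is stronger for anxiety than for anger, since feelings of cancer risk are closer to the former.

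**Working it through.** **The plan's own figure.** The only power statement for linear models (SAP, Sampling Plan, Sample size) is 80% power for an R-squared increment of 1.2%, with 20% explained by other factors, N=500 and alpha 0.05. Effect size: f² = 0.012/(1 − 0.212) = 0.0152. Noncentrality: 500 × 0.0152 = 7.6. Power from the noncentral F with 1 numerator df: 78.6%. This agrees to within two points and is not in dispute. It shows that increments of about 1% are often declared significant at this sample size, so a small spurious component can be enough.

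**Inputs.** N=500 and two-sided 0.05 are from the SAP. The documents give no correlations, so the following are assumptions:

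- a = correlation of affective risk with REDS
- b = correlation of affective risk with anxiety
- c = 0.5 = correlation of REDS with discordance, with discordance related to affective risk only through REDS
- no direct REDS–anxiety link: the two are independent given affective risk

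**Planned model (anxiety on REDS and discordance).** The expected standardised REDS coefficient is β = ab. Its standard error is SE = √[(1 − a²b²)/((N − 3)(1 − c²))]. With z = β/SE, the rate of p<0.05 is Φ(z − 1.96) + Φ(−z − 1.96).

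| a / b | β = ab | SE | z | Rate, formula | Rate, simulation |
|---|---|---|---|---|---|
| 0.10 / 0.10 | 0.01 | 0.0518 | 0.19 | 5.4% | about 6% |
| 0.10 / 0.30 | 0.03 | 0.0518 | 0.58 | 8.9% | about 8% |
| 0.20 / 0.30 | 0.06 | 0.0517 | 1.16 | 21% | 22% |
| 0.25 / 0.40 | 0.10 | 0.0515 | 1.94 | 49% | 48% |
| 0.30 / 0.50 | 0.15 | 0.0512 | 2.93 | 83% | 83% |

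For the last row: SE = √[(1 − 0.0225)/(497 × 0.75)] = √(0.9775/372.75) = 0.0512, and z = 0.15/0.0512 = 2.93.

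**With affective risk added.** If the score is measured without error, the expected REDS coefficient is 0 and the rate is about 5% in every row. With reliability ρ = 0.8 a remainder stays: β = ab(1 − ρ)/(1 − a²ρ).

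- 0.20/0.30: 0.012/0.968 = 0.0124; rate about 6%
- 0.25/0.40: 0.020/0.950 = 0.0211; rate about 7%
- 0.30/0.50: 0.030/0.928 = 0.0323; SE 0.0477, z = 0.68; rate about 10%

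**Sensitivity to how discordance is modelled.** If discordance is instead unrelated to affective risk, the planned-model coefficient becomes ab/(1 − c²). At 0.20/0.30 that is 0.06/0.75 = 0.08, and simulation gives 35% rather than 22%. At 0.30/0.50 it gives 97% rather than 83%, and 14.5% after adjustment at reliability 0.8. The table therefore uses the milder of the two set-ups.

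**Does adjustment remove a genuine effect?** In simulated data where affective risk leads to emotion aroused by the aid, which leads to REDS, adding the score lowered power from 97–100% to 92–100%.

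**The case against.** The other side has real substance.

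- **SH7 is worded as an association**, in a cross-sectional observational survey, and is secondary. A reader might infer that the plan claims to estimate an effect of the aid on emotion, or that SH7 is invalid. The text supports neither. The weakness lies only in reading the association as a response to the aid.
- **Affective risk may be part of the mechanism.** Under the plan's threat-and-efficacy rationale, women high in affective risk react most because the aid feels threatening. Adjustment could then remove genuine reaction. This stands in principle, and it is why both models should be reported. In the simulated chain above the loss was small.
- **The score is not purely prior affect.** The SAP calls it pre-test, but by protocol IV.C it follows the personal risk estimate. It precedes the evidence, not all study information.
- **Much is not visible.** Item wording and timing are not given, and the survey-flow figure is not shown. A reader might infer that no baseline emotion was collected. The documents show only that none is named. The SAP's Measured variables list is weak evidence either way, since it also leaves out the affective risk score.
- **H2 is a joint prediction**, tested by an interaction with screening expectations. The calculation uses a plain linear relation.
- **Weak correlations do little harm.** At 0.1/0.1 the error rate is close to nominal.

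A reader might also take SH7 to be the only analysis bearing on the emotional-versus-cognitive contrast. It is not: H3 also compares discordance with affective risk and screening expectations as predictors of REDS.

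**Conclusion.** The point holds as a modest one about interpretation. The SH7 models omit a score that the plan collects before the evidence and expects to predict REDS, and no pre-aid emotion measure is named. Some of the REDS–anxiety association could therefore be affect that preceded the evidence.

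How much cannot be determined from the documents. Over the assumed range, spurious findings go from near nominal to 83%, with spurious standardised coefficients of 0.01 to 0.15. These figures rest on linear relations, a REDS–discordance correlation of 0.5 and no direct link. The stronger conclusion, that a positive SH7 result would be an artefact, is not supported. It would need sizeable correlations on both sides and items that are not anchored to the information, and the documents establish neither. The point applies mainly to anxiety, touches one secondary hypothesis, and affects no primary one.

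**What to change.** For each SH7 regression, add a second model that includes the mean of the three affective risk questions. Report the REDS and discordance coefficients with and without it. State in the SAP that the association will be attributed to emotion aroused by the aid only if it persists after adjustment. Otherwise it will be reported as an association that prior affective risk may explain. Giving the wording and timing of the anger and anxiety items would let readers judge how far the issue applies.

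The cost is one covariate already collected and a sentence or two in the SAP. There are two downsides. The adjusted coefficient will be somewhat smaller if affective risk is also an antecedent of genuine emotion evoked by the aid. Some confounding will remain if the score is measured with error.
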